9.8. Quality control

HIRA claims data files are large and complex. The study analysis will be thoroughly evaluated and assessed for quality in twofolds: 1) EWU professors with 30+ years of claims data analysis will guide analysts to perform data analyses accurately and efficiently; and 2)

PFIZER CONFIDENTIAL

clinical expert advisors who are leading clinics in mental health in Korea will evaluate the summary statistics of all levels of data and results and will guide correct interpretation.

SAS programs used in the data analysis will be checked and stored to ensure integrity and quality of analysis.

9.9. Limitations of the research methods

Even though HIRA claims data is from the whole population of Korea, the data is not collected for research purpose. Its original purpose was to claim reimbursement. There might be intentional or unintentional miscoding of services performed and diagnosis. These errors are generally undetectable but the dominant majority of data is valid according to the previous studies on the feasibility of Korean NHI claims data.

To reduce chances of including antidepressants use for a disease other than major depressive disorders, operational definitions of at least two outpatient claims or one inpatient claims with diagnosis codes in Table 1 is used. However, it is not 100% accurate since providers are afraid of denial of reimbursement from the HIRA which is empowered with reimbursement review and denial of payment. Hence, in some cases, diagnosis code is put strategically to minimize a chance of denial. For this reason, this study focuses on antidepressants prescribed by a specialist in mental health and only analyze antidepressant prescriptions from other specialists as secondary analysis to identify antidepressant practice patterns from other specialties.

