- Frequency of visit during the first 3 months of acute phase and its relationship to treatment maintenance at 4, 5, 6, 7, 8, 9 month time points and discontinuation rate

3. Choice of antidepressants by non-psychiatric specialty

- o Rheumatology, cardiology, pulmonology, infectious diseases, nephrology, endocrinology and metabolism, gastroenterology, rehabilitative medicine, neurology, neurosurgery, urology, otorhinolaryngology, gynecology & obstetrics, etc.

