9.7. Data analysis

The proportions and drug utilization patterns comparisons of 11 study drugs will use all the patients satisfying inclusion and exclusion criteria (raw data). Adherence, persistence, discontinuation, recurrence, and adverse outcomes comparison of 11 study drugs will use both raw data and matched data where patients will be matched on demographic and clinical characteristics. All outcome variables will be summarized *descriptively* through the tabular and graphical display of mean values, medians, ranges and standard deviations of continuous variables of interest and frequency distributions of categorical variables. Safety outcomes of treatments will be estimated from time-to-event models. The 95% confidence intervals for the estimates will be calculated and $p < 0.05$ will be considered significant. All analyses will be carried out using SAS version 9.4 which is installed on HIRA server. Analysis and reporting will be compliant with Strengthening the Reporting of Observational Studies in Epidemiology (STROBE) recommendations.

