2.2 STUDY OBJECTIVES

Primary objectives:

1. Explore baseline characteristics and drug utilization patterns of 11 commonly used antidepressant therapy during 90 days of acute treatment phase
 - Top 11 commonly used antidepressants according to local market data are as follows:
 - Escitalopram, paroxetine, fluoxetine, mirtazapine, duloxetine, sertraline, venlafaxine, tianeptine, vortioxetine, desvenlafaxine, bupropion
 - Proportion of antidepressants prescribed by sex, age (<20, 21-64, > 65), sex and age combined
 - Initial doses used, average daily doses of each antidepressants
 - Average length of treatment with index medication before therapy change occurs (switching, combination, augmentation, discontinuation)
 - Adherence and persistence measured by medication possession ratio during first 90 days of treatment period
2. Explore drug utilization patterns such as therapy changes, medication compliance and recurrence relationship, and risk of adverse outcomes during maintenance phase
 - The choice of antidepressant, average length of new treatment maintenance, average number of co-administered medications (e.g., atypical antipsychotics, mood stabilizer, thyroid hormone, psychostimulant) when following changes occur from initial monotherapy:
 - Switching
 - Combination
 - Augmentation
 - Medication compliance and recurrence
 - Compliance measured as adherence and persistence
 - Recurrence
 - Relationship between recurrence and compliance

PFIZER CONFIDENTIAL

- *Risk of adverse outcomes measurement between individual ADs that are well known to be treatment-related (e.g., hyponatremia, GI bleeding, fractures, falls, risk of intracranial hemorrhage, attempted suicide/self-harm, myocardial infarction, epilepsy/seizures, stroke/transient ischemic stroke)*

Secondary objectives:

1. *Choice of antidepressants and drug utilization patterns in patients with various comorbidities*
 - *Psychiatric comorbidities*
 - *Mild cognitive impairment (MCI)*
2. *The relationship of non-pharmacologic treatment and discontinuation, medication compliance*
 - *Non-pharmacologic treatments may include: cognitive behavioral therapy (CBT), frequency of physician visit during acute and maintenance phase of treatment*
 - *Frequency of visit during the first 3 months of acute phase and its relationship to treatment maintenance at 4, 5, 6, 7, 8, 9 month time points and discontinuation rate*
3. *Choice of antidepressants by non-psychiatric specialty*

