4 ANALYSIS SETS/POPULATIONS

4.1 FULL ANALYSIS SET

Subjects who newly initiated antidepressant therapies between Jan 01, 2018 to Jun 30, 2019 in the Health Insurance Review and Service (HIRA) database

** Index date is the first prescription date of study drugs, including SSRIs, SNRIs, and other ADs during the intake period (Jan 01, 2018 to Jun 30, 2019).*

Inclusion criteria

Patients must meet all of the following inclusion criteria to be eligible for inclusion in the study:

1. *Patients aged 18 years or older and 70 years or younger on the index date*
2. *Patients who had at least one inpatient claim or two outpatient claims in the intake period with any of the following diagnosis codes:*

PFIZER CONFIDENTIAL

Table 1. Diagnosis Codes for Inclusion

KCD-7 Code ¹⁾	Description
F06.3	Organic mood[affective] disorders
F32*	Depressive episode
F33*	Recurrent depressive disorder
F34.1	Neurotic depression
F38.1	Other recurrent mood[affective] disorders
F41.2	Mixed anxiety and depressive disorder

1) KCD-7 = Korean version of ICD-10

3. Patients prescribed any of the following antidepressant during intake period (from January 1, 2018 to June 30, 2019)

Table 2. Study Drug List

Active Ingredient	Dosage	HIRA Drug Main Ingredient Codes
Escitalopram	5mg	474801ATB
	10mg	474802ATB
	20mg	474803ATB
	15mg	474804ATB
	10mg	521101ATD
	20mg	521102ATD
Paroxetine	10mg	209301ATB
	20mg	209302ATB
	12.5mg	209304ATR
	25mg	209305ATR
Fluoxetine	10mg	161501ACH
	10mg	161501ATB
	20mg	161502ACH
	20mg	161502ATB
	20mg	161502ATD
Mirtazapine	15mg	196201ATB
	15mg	196201ATD
	30mg	196202ATB
	30mg	196202ATD
	7.5mg	196204ATB
	7.5mg	196204ATD
Duloxetine	30mg	495501ACE
	30mg	495501ATE
	60mg	495502ACE
	60mg	495502ATE
Sertraline	50mg	227001ATB
	0.1g	227002ATB
Venlafaxine	75mg	247502ACR
	37.5mg	247504ACR
Tianeptine	12.5mg	229601ATB
Vortioxetine	5mg	628501ATB
	10mg	628502ATB
	15mg	628503ATB

PFIZER CONFIDENTIAL

	20mg	628504ATB
Desvenlafaxine	50mg 100mg	626401ATR 626402ATR
Bupropion	0.1g 0.15g 0.3g	428101ATB 428102ATR 428103ATR

Exclusion criteria

1. Patients meeting any of the following criteria will not be included in the study:
2. Patients with a claim of diagnosis codes in Table 1 during the 12 month pre-index period
3. Patients with a claim of prescription in Table 2 during the 12 month pre-index period

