7.2 STATISTICAL ANALYSES

7.2.1 Study Drug Analysis in Acute Phase

- To understand the top 11 antidepressants usage among the Korean patients with depression in acute treatment phase
- Primary analysis
- Endpoints:
 - Proportion of 11 antidepressants, by age (<20, 21-64, > 65), by gender, by age and gender
 - Choice of index drug
 - Initial doses used, average daily doses of each antidepressant
 - The average length of treatment with index medication before therapy change occurs (switching, combination, augmentation, discontinuation)
 - Adherence measured by medication possession ratio and persistence during first 90 days and 180 days of treatment period, respectively
- Population: patients who meet inclusion criteria and exclusion criteria in section 4.1 and classified by the index antidepressant out of 11 top antidepressants in the Korean market (Table 2)
- Significance on continuous variables will be tested by ANOVA (if equal variance condition satisfied) or the Kruskal-Wallis H test (otherwise). Provider specialty and other patient characteristics will be used to fit antidepressant choice by multivariate logistic regression analysis of each study drug choice.
- Covariates: antidepressant class covariates such as SSRIs, SNRIs, and other ADs will be used as grouping variables.
- Missing values will be dropped from the analysis
- The role of this analysis is to provide information on study antidepressants in the acute phase of drug therapy for Korean patients with depression.

PFIZER CONFIDENTIAL

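### Protocol 9.9 makes mental-health-specialist prescribing the main analysis, but no eligibility rule or primary analysis set applies this, and the SAP does not acknowledge the conflict

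*Protocol*

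**What the plan says.** **Prescriber.** Protocol 9.9 first relies on the requirement of two outpatient claims or one inpatient claim with a listed depression code. It then concedes that this rule is imperfect, because providers sometimes select codes with reimbursement in mind. Its answer is that "this study focuses on antidepressants prescribed by a specialist in mental health and only analyze antidepressant prescriptions from other specialists as secondary analysis". Secondary objective 3 in Protocol 8, "Choice of antidepressants by non-psychiatric specialty", fits that split.

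The operative sections say something else. Protocol 9.2.1 and 9.2.2 contain no specialty criterion. Protocol 9.7 states that the comparisons of proportions and utilization patterns "will use all the patients satisfying inclusion and exclusion criteria (raw data"). SAP 4.1 has no specialty criterion either. The population for SAP 7.2.1, a primary analysis, is "patients who meet inclusion criteria and exclusion criteria in section 4.1 and classified by the index antidepressant", and SAP 7.2.2 continues with those of them who reach the maintenance phase.

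**Washout.** SAP 4.1 describes the cohort as "Subjects who newly initiated antidepressant therapies between Jan 01, 2018 to Jun 30, 2019". The drug exclusion is narrower: "Patients with a claim of prescription in Table 2 during the 12 month pre-index period". Table 2 lists 11 ingredients, introduced in SAP 2.2 with the words "Top 11 commonly used antidepressants according to local market data are as follows".

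**The concern.** The restriction in 9.9 is the protocol's own response to a weakness that it admits in its case definition. Someone who reads 9.9 will take the primary results as describing depression treated by mental-health specialists. Someone who programs from SAP 4.1 and 7.2 will produce results for all prescribers. The two populations can differ in how many patients truly have depression and in how long they stay on treatment.

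Persistence, discontinuation, adherence, recurrence and adverse outcomes are all primary and are all tabulated by drug. If the drugs differ in who prescribes them, differences in specialty mix will appear in the raw tables as differences between drugs.

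The washout raises a smaller question of the same kind. A patient who took an unlisted antidepressant in the previous year, without a Table 1 code, is counted as a new starter. That patient's index prescription may really be a switch or an addition.

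**Working it through.** The first check is a comparison of text, because no sample-size, power or error-rate figure in the documents bears on the point.

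**Where prescriber specialty appears**

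| Place | Role of specialty |
|---|---|
| Protocol 9.9 | Defines the main focus; other specialties secondary |
| Protocol 8, secondary objective 3 | Non-psychiatric specialties as a secondary topic |
| Protocol 9.2.1, 9.2.2 | None |
| Protocol 9.7 | None; all eligible patients, or matched patients |
| SAP 1 (change table) | None; no change logged |
| SAP 4.1 | None |
| SAP 4.4 | A subgroup that may be considered |
| SAP Table 3 | One of the listed covariates |
| SAP 7.2.1, 7.2.2 (primary) | Predictor in the drug-choice models |
| SAP 7.2.5 (secondary) | Stratifier, but only in patients with a prespecified comorbidity |

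Using specialty as a predictor in 7.2.1 and 7.2.2 makes sense only if several specialties are in the primary cohort. The SAP therefore does intend all prescribers. SAP 7.2.5 does not restore the split in 9.9, because it draws on the same all-prescriber population and then cuts it by comorbidity.

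**Size, on assumptions only.** The documents give neither the share of non-specialist index prescriptions nor outcomes by specialty. Let *s* be the non-specialist share, *p* the outcome percentage under specialists, and *p + d* the percentage otherwise.

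- Pooled percentage = (1 − s)p + s(p + d) = p + s·d, so the shift is s·d.
- Assumed s = 10% and d = 10 points: 0.10 × 10 = 1 point.
- Assumed s = 40% and d = 30 points: 0.40 × 30 = 12 points.
- For two drugs with no true difference, the raw gap is (s_A − s_B)·d. With assumed shares of 50% and 10% and d = 20 to 30 points, the gap is 0.40 × 20 = 8 to 0.40 × 30 = 12 points.

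These figures show how the mechanism works. They do not estimate its effect in this study.

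**Washout.** Two 12-month exclusions apply before the index date: one for Table 1 diagnoses and one for Table 2 drugs. A prior user of an unlisted antidepressant who had a Table 1 code is removed by the first. One treated under another code passes both. The gap is therefore confined to that second group, whose size the documents do not give.

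**The case against.** The strongest reply is that the SAP has dropped nothing. A reader might infer that it removed a protocol restriction, but Protocol 9.2 never contained one, and 9.7 already names all eligible patients. The SAP follows the operative sections, and the conflict lies inside the protocol, between a limitations paragraph and the eligibility and analysis sections. This stands. What remains is that the SAP settles the conflict without saying so.

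A reader might also infer that nothing protects against miscoded depression. That goes too far, because SAP 4.1 keeps the claim-count rule. Only the second layer is missing.

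Next, specialty is a Table 3 covariate, SAP 7.1 plans propensity-score matching and weighting, and Protocol 9.7 promises matched as well as raw results for the main outcomes. This helps only in part. The covariates that SAP 7.1 names as examples do not include specialty, the final list is left to analysis development, and raw comparisons are still reported. Balancing specialty between drugs also does not remove patients whose depression code was chosen for payment, which is the problem that 9.9 addresses.

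The study is exploratory and states no hypotheses. That lowers the stakes, but the primary population still has to be identifiable.

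On the washout, it might be inferred that the SAP weakened the protocol. It did not: the exclusion has the same wording in Protocol 9.2.2, and the index date is defined on the study drugs. The mismatch is with the cohort's label, and the diagnosis washout narrows it.

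**Conclusion.** The point holds as an unreconciled conflict over the primary population. Protocol 9.9 describes a specialist-based main analysis. Protocol 9.2 and 9.7 and SAP 4.1, 7.2.1 and 7.2.2 specify an all-prescriber one, and nothing records a choice between them. As planned, the raw primary results by drug combine specialist and non-specialist prescribing. The documents support neither a numerical bias nor a claim that the results will be misleading. The 1 to 12 point shift rests wholly on assumed shares and assumed outcome differences.

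The washout limited to Table 2 is a valid but secondary point about what may be called new initiation. How far it can be corrected depends on whether claims for unlisted antidepressants were extracted, which the documents do not say.

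**What to change.** 1. In SAP 4.1, define a specialist-prescribed set as patients whose index prescription came from a mental-health specialist. Use it for the primary outcome analyses in 7.2.1 and 7.2.2, as 9.9 states, and report all prescribers as secondary.
2. Keep the drug-choice models that use provider specialty, and 7.2.5, in the all-prescriber set. In a specialist-only set that predictor would have little left to explain.
3. If the sponsor prefers all prescribers as primary, amend Protocol 9.9, log the decision in SAP Section 1, and report a specialist-only analysis of every primary outcome alongside.
4. Extend the 12-month drug exclusion to all antidepressant ingredient codes if those claims are in the extract. If they are not, describe the cohort as new users of the 11 study drugs.

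**Cost.** Specialty is already a planned variable, so the first change is one filter and some SAP text. The primary cohort becomes smaller. The only size figure is 752,190 patients over 2011 to 2015 in a previous study. Pro rata to the 18-month intake this is 752,190 / 5 × 1.5 = 225,657, a rough guide only, since it comes from another period and does not reflect the SAP's upper age limit of 70. A restricted set would probably still be large, but its size should be counted. Because the SAP was already being amended during data analysis, any change of primary set must be logged as made at that stage.

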9.10. Other aspects

Not applicable.

10. PROTECTION OF HUMAN SUBJECTS

10.1. Patient information

This study involves data that exist in anonymized structured format and contain no patient personal information.

10.2. Patient consent

As this study involves anonymized structured data, which according to applicable legal requirements do not contain data subject to privacy laws, obtaining informed consent from patients by Pfizer is not required. An exemption of informed consent will be sought from the EWU IRB and the approval will be forwarded to Pfizer.

PFIZER CONFIDENTIAL

10.3. Institutional review board (IRB)/Independent ethics committee (IEC)

An exemption of IRB review will be sought from the EWU IRB and the approval will be forwarded to Pfizer..

10.4. Ethical conduct of the study

The study will be conducted in accordance with legal and regulatory requirements, as well as with scientific purpose, value and rigor and follow generally accepted research practices described in Guidelines for Good Pharmacoepidemiology Practices (GPP) Good Practices for Outcomes Research issued by the International Society for Pharmacoconomics and Outcomes Research (ISPOR), Good practices for real-world data studies of treatment and/or comparative effectiveness: Recommendations from the joint ISPOR-ISPE Special Task Force on real-world evidence in health care decision making, International Ethical Guidelines for Epidemiological Studies issued by the Council for International Organizations of Medical Sciences (CIOMS), European Medicines Agency (EMA) European Network of Centres for Pharmacoepidemiology and Pharmacovigilance (ENCePP) Guide on Methodological Standards in Pharmacoepidemiology, The ENCePP Code of Conduct for scientific independence and transparency in the conduct of pharmacoepidemiological and pharmacovigilance studies, Food and Drug Administration (FDA) Guidance for Industry: Good Pharmacovigilance Practices and Pharmacoepidemiologic Assessment, FDA Guidance for Industry and FDA Staff: Best Practices for Conducting and Reporting Pharmacoepidemiologic Safety Studies Using Electronic Healthcare Data and FDA Guidance for Industry: Patient-Reported Outcome Measures: Use in Medical Product Development to Support Labeling Claims.

11. MANAGEMENT AND REPORTING OF ADVERSE EVENTS/ADVERSE REACTIONS

This study involves data that exist as structured data by the time of study start or a combination of existing structured data and unstructured data, which will be converted to structured form during the implementation of the protocol solely by a computer using automated/algorithmic methods, such as natural language processing.

In these data sources, individual patient data are not retrieved or validated, and it is not possible to link (i.e., identify a potential association between) a particular product and medical event for any individual. Thus, the minimum criteria for reporting an adverse event (AE) (i.e., identifiable patient, identifiable reporter, a suspect product, and event) cannot be met.

12. PLANS FOR DISSEMINATING AND COMMUNICATING STUDY RESULTS

The results of this research will be submitted for publication in scientific peer-reviewed journals and for presentation at appropriate research conferences in either poster or podium presentation,

Authorship of any publications resulting from this study will be determined on the basis of the International Committee of Medical Journal Editors (ICJME) Recommendations for Conduct, Reporting, Editing and Publication of Scholarly Work in Medical Journals:

- Authorship credit should be based on (1) substantial contributions to conception and design, acquisition of data, or analysis and interpretation of data (2) drafting the article or revising it critically for important intellectual content; (3) final approval of the version to be published and (4) agreement to be accountable for all aspects of the work in ensuring that questions related to the accuracy or integrity of any part of the work are appropriately investigated and resolved. Authors should meet conditions 1, 2, 3 and 4.

[figure not shown]
All publications based on this study must be submitted to Pfizer for corporate review. The vendor agreement will detail the procedures for, and timing of, Pfizer's review of publications.

In the event of any prohibition or restriction imposed (e.g., clinical hold) by an applicable competent authority in any area of the world, or if the party responsible for collecting data from the participant is aware of any new information which might influence the evaluation of the benefits and risks of a Pfizer product, Pfizer should be informed immediately.

ANNEX 1. LIST OF STAND ALONE DOCUMENTS

None

ANNEX 2. ENCEPP CHECKLIST FOR STUDY PROTOCOLS

Not applicable

ANNEX 3. ADDITIONAL INFORMATION

Not applicable

PFIZER CONFIDENTIAL

1 AMENDMENTS FROM PREVIOUS VERSION(S)

- The status of the study when the amendment is made: During data analysis
- Details and rationale of the changes to the SAP:

Change	Before	After	Rationale
The period of data acquisition	01 Jan 2016 ~ 31 Dec 2019	01 Jan 2017 ~ 31 Dec 2020	To acquire and analyze the latest data available due to the delay of the data acquisition
Inclusion criteria	Patients aged \geq 18 years on the index date	Patients aged \geq 18 years and \leq 70 years on the index date.	Due to a considerable incidence of depression resulting from concomitant diseases in the elderly and limitation of data capacity
MPR	Calculated by (Days of medication possession from the prescriptions filled in the 90 days) / (90 days + extra days of drug supply from the last prescription fill during the 90 days)	Calculated by (Days of medication possession from the prescriptions filled in the 180 days) / (180 days + extra days of drug supply from the last prescription fill during the 180 days)	To lead to more reasonable results that reflects the real-world situation
Operational definition of 'persistence'	For each of 11 study drugs, the average length of treatment on the index drug (allowing a 14-day permissible gap) will be calculated	For each of 11 study drugs, the average length of treatment on the index drug during the first 180-day period (allowing a 14-day permissible gap) will be calculated	Same as above
Operational definition of 'adherence'	For each of 11 study drugs chosen as index drug, adherence will be measured by MPR during the first 90-day period from the index date (acute treatment phase)	For each of 11 study drugs chosen as index drug, adherence will be measured by MPR and persistence during the first 90-day and 180-day period from the index date, respectively (acute treatment phase) - MPR \geq 0.75 and persistence \geq 90 will be considered as adherence	Same as above
Operational definition of 'recurrence'	Recurrence was operationally defined as either one of the following being satisfied: 1) Inpatient episode with a diagnosis code in Table 1 2) Emergency room visit with a diagnosis code in Table 1 Suicide attempt identified by the following KCD-7 codes (the rest omitted)	Recurrence during the acute treatment phase was operationally defined as either one of the following being satisfied: 1) Inpatient episode with a diagnosis code in Table 1 2) Inpatient episode via the department of psychiatry or emergency medicine 3) Inpatient episode via nursing hospital	Same as above

PFIZER CONFIDENTIAL

		
4) Emergency room visit with a diagnosis code in Table 1
 
5) Suicide attempt identified by the following KCD-7 codes (the rest omitted)
 
6) Augmentation of the following non-AD drugs
 
 - Antipsychotic: amisulpride, ariprazole, olanzapine, quetiapine, risperidone, perphenazine - Anticonvulsant: carbamazepine, valproic acid, lamotrigine - Mood stabilizer: lithium - Anxiolytic: buspirone - Thyroid hormone: levothyroxine, liothyronine 
Recurrence after the acute treatment phase was operationally defined as either one of the following being satisfied:
 
1) ~6) the same as above
 
7) AD prescription after 30 days of drug holiday
	
--	--	---	--

